GCP	Good Clinical Practice
GDPR	General Data Protection Regulation; in Dutch: Algemene Verordening Gegevensbescherming (AVG)
G8	Geriatric-8
HR	Heart Rate
HRV	Heart rate variability
IADL	Instrumental activities of daily living
IB	Investigator's Brochure
IC	Informed Consent
IMP	Investigational Medicinal Product

IMPD	Investigational Medicinal Product Dossier
IMD	Investigation with Medical Device
IMDD	Investigational Medical Device Dossier
ISI	Insomnia Severity Index
IQR	Interquartile Range
METC	Medical research ethics committee (MREC); in Dutch: medisch-ethische toetsingscommissie (METC)
LUMC	Leiden University Medical Center
MCTQ	Munich Chronotype Questionnaire
MET	Metabolic Equivalent of a Task
Mg	Miligravity
MRI	Magnetic Resonance Imaging
PAI	Physical Activity Index
PBMC	Peripheral Blood Mononuclear Cell
PPG	Photoplethysmography
QOL	Quality Of Life
RET	Resistance Exercise Training
(S)AE	(Serious) Adverse Event
SCN	Suprachiasmatic Nucleus
SD	Standard Deviation
SPC	Summary of Product Characteristics; in Dutch: officiële productinformatie IB1-tekst
Sponsor	The sponsor is the party that commissions the organisation or performance of the research, for example a pharmaceutical company, academic hospital, scientific organisation or investigator. A party that provides funding for a study but does not commission it is not regarded as the sponsor, but referred to as a subsidising party.
SUSAR	Suspected Unexpected Serious Adverse Reaction
SQUASH	Short Questionnaire to Assess Health enhancing Physical Activity
UAVG	Dutch Act on Implementation of the General Data Protection Regulation; in Dutch: Uitvoeringswet AVG
WMO	Medical Research Involving Human Subjects Act; in Dutch: Wet Medisch-wetenschappelijk Onderzoek met Mensen

SUMMARY

Rationale: There are indications based on epidemiological cohort studies and animal experiments that timing of physical activity (also referred as “ chronoactivity”), irrespective of intensity, impacts health status and disease risk. Here, we hypothesize that timing of physical activity has a beneficial impact on insomnia symptoms and related circadian health parameters (e.g., metabolic, psychosocial) in older people.

Objective: Main: To examine the effect of physical activity timing on insomnia severity in older adults with self-reported sleep problems.

Additional: To examine the effect of physical activity timing on exploratory rhythmic parameters of biological clock function, physiology and metabolism, mental health, behavioural factors, and immune and cell signalling functions.

Study design: Randomised cross-over study.

Study population: 40 community dwelling older adults aged between 60 and 80 years old with long-lasting (≥ 3 months) self-reported sleep problems from Leiden and surrounding areas in close proximity to the study center.

Intervention: The intervention will comprise one sedentary period and two periods of increased physical activity with different daily patterns: 1) active morning; 2) active evening; with a duration of 14 days each. In both active intervention arms, participants will follow 8 coached outdoor physical exercise sessions (Vitality Club) comprising endurance and strength exercises. The training sessions will be held first either in the morning or evening (depending on the intervention arm) and will be one hour long. On days participants are not able to attend the Vitality Club, they will be asked to follow the ‘Active@Home’ program; a 1-hour training session of various moderate to vigorous activities. Since this will be a randomized cross-over study, all participants will follow the sedentary period as well as both exercise timing interventions consecutively with a 7-day wash-out period between all interventions.

Main study parameters/endpoints: The primary outcome is change in insomnia severity as measured by the Insomnia Severity Index (ISI). Secondary outcomes parameters include multiple components of objective sleep quality measured with the Withings Sleep Analyzer, tri-axial accelerometry and subjective sleep quality questions as well as circadian and diurnal patterns of melatonin, heart rate, heart rate variability, breathing rate, oxygen saturation, core body temperature, EMA, and objective emotional arousal and stress. Additionally, we will observe eating patterns (timing and overall intake). Finally, blood will be sampled at baseline and after each intervention and stored for measurements of metabolic and physiological functioning and expression of genes involved in the regulation of the biological clock.

Nature and extent of the burden and risks associated with participation, benefit and group relatedness: Blood sampling, explanation of use of the measurement devices and the

assessment of participants well-being will be done by a trained nurse at the LUMC and at home to minimize burden for participants. During the complete study duration, participants will wear one wrist-worn wearable that is capable of measuring multiple physiological aspects in the participant. Moreover, participants are asked to perform three series of seven consecutive saliva swabs on set times on the last day of each intervention and they will be asked to rank their mood as well as log their meals multiple times a day. The risks of this study are considered minimal since this is a lifestyle intervention and only minimally invasive procedures are used (venous blood sample which may cause a small hematoma) that can be considered routine medical practice and are known to carry only minimal risks. The study may cause some burden since participants are required to change and monitor their daily routine for a longer period (42 non-consecutive days) of time.

1. INTRODUCTION AND RATIONALE

Essentially all biochemical, physiological and behavioural processes are orchestrated by circadian rhythms to respond to the 24-hour day/night cycle. Processes such as energy metabolism, hormone levels, sleep wake cycles, core body temperature are strongly governed by circadian rhythms.(1) Proper functioning according to the light/dark cycle of all bodily functions relies on the suprachiasmatic nucleus (SCN) also known as the central clock which is located directly behind the eyes in the anterior hypothalamus and primarily responds to light.(1) The SCN determines the phase of peripheral clocks through a variety of signalling relays.(2)

A good running circadian clock is associated with (healthy) longevity.(3) Yet, proper circadian organization (also referred as “circadian health”)(4) is threatened by our modern day 24-hour society. Shift work, social jetlag, increased exposure to blue-light emitting devices and globalization of a 24/7 society facilitated by advancing technology and social media, jeopardize a healthy biological rhythm.(4)

When internal circadian rhythms, which are normally approximately 24-hour cycles, are not synchronised with the environment or each other, disruption of circadian and diurnal rhythms can occur.(5) This ‘desynchrony’ occurs when behaviours such as physical activity, sleep, food intake, and exposure to light are not at an appropriate time relative to the central circadian clock.(5) Another cause of circadian misalignment or desynchrony is ageing. A substantial amount of studies shows the deterioration of the biological clock with increasing age (**Figure 1**).^(1, 3, 6) Studies consistently show that experimental disruption or desynchronization of circadian rhythms has detrimental effects on health and lifespan.^(7, 8) Our decreasing circadian health may be partly responsible for the rising prevalence of sleep problems in (older) adults. In the Netherlands, 20% of all people of 12 years and older have self-reported sleep problems and even 28% of older adults aged 75 years and older.⁽⁹⁾ Additionally, and perhaps through the pathway of poor sleep, clear associations of circadian misalignment are observed with cancer onset, cardiometabolic diseases such as obesity, diabetes, heart disease, and stroke, and neurologic disease such as depression, Parkinson disease, dementia, and sleep disorders.^(4, 5, 10, 11)

‘Zeitgebers’, which are defined as regular cyclic environmental signals and which include food intake, light

[figure not shown]

Figure 1. Effect of ageing on circadian rhythms (Liu et al.)⁽¹⁾

exposure, and physical activity, can calibrate our circadian clock.(12, 13) Regular physical activity is known to positively affect the circadian clock and is associated with healthy ageing.(13, 14) Guidelines indicate the required intensity, frequency and duration of physical activity to maintain or achieve health. However, less is known about the best timing of physical activity. A growing field of research on 'chronobehaviour', (timing of lifestyle behaviours) already marks the importance of timing of food intake and light exposure.(4, 15-21) Yet, intervention studies on 'chronoactivity' (timing of physical activity) are largely lacking. Ideally, enriching current guidelines by adding the timing component of physical activity might improve these guidelines and facilitate for more effective physical activity and faster improvement of health outcomes such as recovering from a period of worse sleep.

Several studies in mice reported that exercise restores circadian heart rate and body temperature in mice with central circadian disruption.(22, 23) Additionally, studies in humans have revealed exercise stimulates the expression of core clock genes. Observational studies that specifically focussed on chronoactivity, demonstrate associations between morning physical activity and increased metabolic health,(24) increased cardiometabolic fitness,(25) and even an approximately 15% lower risk of incident atherosclerotic cardiovascular and cerebrovascular disease(26). Moreover, there are some intervention studies in this field.(27-29) However, their results are inconclusive. Multiple studies show the seemingly positive effect of morning physical activity on body composition and metabolic health.(29, 30) Contrarily, several studies show opposite findings indicating that evening exercise had positive effects on heart rate recovery, blood pressure, and blood glucose levels.(27, 28, 31). One of these even stated that morning physical activity had a deleterious effect on blood glucose levels in diabetic men.(27) This contrariety in existing literature could be partly explained by 1) different study outcomes, 2) different measurement methods and definitions of physical activity, and 3) small sample sizes and specific groups (e.g., diabetic men or menopausal women) in which the studies have been conducted. Nevertheless, these studies suggest that timing of physical activity serves as an important Zeitgeber, and changes the phase of the molecular clock, specifically in peripheral tissues.(22) Yet, despite the increasing interest and mounting evidence for chronoactivity, the optimal circadian timing of physical activity for circadian health remains unclear and little is known about the influence of chronoactivity in older adults which most frequently suffer from sleep problems.(9)

In view of the detrimental effects of circadian misalignment, the large group of older people suffering from sleep problems, and the seeming importance of chronoactivity, we will perform a randomised cross-over study that aims to uncover the effect of timing of physical activity on insomnia severity and related (circadian) health parameters in older adults with self-reported sleep problems.

2. OBJECTIVES

Primary Objective

To examine the effect of physical activity timing on insomnia severity in older adults with self-reported sleep problems.

Secondary Objective

To explore the effect of physical activity timing on rhythmic parameters of biological clock function, physiology and metabolism, mental health, behavioural factors, and immune and cell signalling functions.

3. STUDY DESIGN

We will perform a randomized two-armed cross-over study. Both groups will start with the sedentary period. Randomization will be performed at the moment of enrollment using a computer-based statistical program (depending on the intervention arm, participants will then undergo the active morning intervention or active evening intervention first, followed by the remaining intervention. There will be a total of two washout periods both lasting 7 days, one between the sedentary period and first intervention and one between the first and second intervention to prevent or minimize 'carry over' of previous intervention effect. The two interventions and the sedentary period will last 14 days each and contain a 'calibration period' (7 days) and a 'measurement week' (7 days). The former will serve as an adjustment period in which we hypothesize that our endpoints of interest will adjust to the new exercise regimen. After the calibration period, the measurement week starts in which all endpoints will be measured. Apart from the measurements, there are no differences in intervention between calibration and measurement week. The total study duration will be 8 weeks and the study will largely take place at the participants' home except for the training sessions (Vitality Clubs) that will take place at an outdoor sports facility in the municipality of Leiden and the study site visits which will take place in the LUMC. **Figure 3.1** shows a schematic overview of the study outline and **Appendix A** shows an example of the study schedule during the active morning intervention.

[figure not shown]

Figure 3.1. Schematic overview of the study

3.1 Design justification

A cross-over study allows the response of a participant to morning exercise to be contrasted with the same participant's response to evening physical activity and sedentary period. Removing inter-participant variation allows for more efficient and precise estimation than similar sized studies with parallel intervention groups.

As we study the effect of timing on change in insomnia severity and changes in the rhythm of multiple processes hypothesized to be altered rapidly through environmental cues, such as daylight changes over the season, a randomized cross-over study which is usually bound to short-term outcomes is the most suitable design for this study.

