4.4 Sample size calculation

The sample size was calculated for the primary outcome of mean change of insomnia symptoms severity from baseline and after completing the active morning vs. active evening measured by the ISI which is proven to be a well validated and sensitive questionnaire for mapping insomnia severity. All sample size calculations were based on statistical power of 0.80 and a 2-sided α of 0.05. The calculations were performed using GPower v.3.1 (Kiel University, Germany). To the best of our knowledge, there is no literature available on the effect size of physical activity timing on insomnia severity. Therefore, estimations were based on treatment effect size of guideline recommended physical activity on insomnia severity (measured by ISI) found in a previous randomized controlled trial(32). Assuming a standard deviation (SD) of 5.4, a total of 36 participants are required to detect a minimal difference of 2.6 points on the ISI. Considering a possible dropout rate of 10% during the study, the target sample size is 40 participants.

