
5.1.1 Sedentary period

Literature shows that physical activity improves insomnia severity.(32) In previous studies, the follow-up period was at least 3 months. As we will use a shorter follow-up period in this study, we have included a sedentary period, to assess the effect of physical activity versus no physical activity. This intervention additionally examines the effect of physical activity timing. In order to verify that the exercise intervention provided in this study has a similar positive effect, we will compare our interventions to this sedentary period. All participants will start with a 14-day sedentary period. They will be instructed to refrain from any moderate to vigorous exercise. Compliance to these instructions will be observed through the wrist worn accelerometer. Where necessary, participants will be reminded of the instructions.

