10.2 Secondary study parameter(s)

Secondary endpoints include changes in:

Biological clock function

- Clockgene expression
- Core body temperature (°C)
 - Diurnal pattern
 - Time of lowest temperature
- Melatonin
 - Dim light melatonin onset (DLMO)

Physiological parameters

- Heart rate
 - Diurnal pattern
 - Average
 - Resting heart rate
 - Minimum/peak heart rate (5 and 95 percentile)
- Heart rate variability (HRV)
- Breathing rate
- Oxygen saturation (SpO2)

Mental health

- Subjective mood
 - Diurnal pattern of:
 - Positive affectivity
 - Negative affectivity
 - Energy
 - Fatigue

- Cognition
- (objective) Electrodermal activity (emotional arousal and stress)

Behavioural factors

- Food intake
 - Frequency
 - Timing
- Habitual sleep (**Table 8.1**)
 - Sleep latency (min)
 - Duration (min)
 - Efficiency (%)
 - Sleep phases (%, min)
 - Awakenings at night (x, min)
 - Rested feeling (subjective, 0-7)
 - General satisfaction with sleep (subjective, 0-7)

Biochemistry

- Glucose metabolism
- Inflammatory markers
- Liver function
- Kidney function
- Thyroid function
- Bone metabolism markers
- White blood cell count

Changes between active morning and active evening will be assessed. Diurnal patterns will be calculated through the hourly mean level of for example glucose and will be displayed for each condition. Additionally, we will perform sensitivity analysis for both the primary endpoint as all secondary endpoints by analyse the changes between the sedentary period & active morning, and the sedentary period & active evening. Assuming the data is normally distributed, a paired t-test will be used for all analyses and data will be shown in as mean difference, SD, and p-value.

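### The activity-versus-no-activity question is tested only as two separate comparisons; a contrast on the mean of both active periods should be added beside them

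*Combined protocol and SAP*

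**What the plan says.** Section 3.1 says that the cross-over allows a participant's response to morning exercise "to be contrasted with the same participant's response to evening physical activity and sedentary period". The sedentary-period part of section 5.1.1 gives the purpose: "we have included a sedentary period, to assess the effect of physical activity versus no physical activity". It adds that the comparison should verify that this programme has a positive effect like that in earlier, longer studies. It also says that the period serves the timing question and that the interventions, in the plural, will be compared with it.

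Section 8.3.1 has the ISI completed on the last day of each of the three periods, so each participant gives one sedentary and two active scores. By sections 3 and 8.2, the sedentary period comes first for everyone and only the order of the active periods is randomised.

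Section 10.2 labels the sedentary comparisons sensitivity analyses, for the primary and all secondary endpoints. It will "analyse the changes between the sedentary period & active morning, and the sedentary period & active evening", and "a paired t-test will be used for all analyses", reported as mean difference, SD and p-value. No section describes a combined active-versus-sedentary contrast or says how to read the two results if they differ. The primary test in section 10.1 is morning against evening only.

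**The concern.** Whether this exercise programme improves insomnia within two weeks is one question, and both active scores bear on it. Two separate tests each leave one active score unused, so each estimate of the exercise effect is less precise than the data allow.

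Two tests can also split. One may be significant and the other not when both timings have the same effect, and the plan gives no rule for that case. This matters most if the primary morning-evening comparison is null, because the reader then needs to know whether both timings helped or neither did. A split pair does not answer that, and it invites the reading that only one timing works.

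**Working it through.** **Inputs.** From section 4.4: "All sample size calculations were based on statistical power of 0.80 and a 2-sided α of 0.05"; "Assuming a standard deviation (SD) of 5.4, a total of 36 participants are required" "to detect a minimal difference of 2.6 points on the ISI"; and "Considering a possible dropout rate of 10% during the study, the target sample size is 40 participants". The documents do not give the covariance between periods, so it is an assumption here.

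**The plan's own figure.** With a paired t-test and noncentral t, the standardised difference is 2.6/5.4 = 0.481. This gives n = 36 with power 0.802, and 36/0.90 = 40. Reading 5.4 as a between-person SD in a two-sample formula gives 68 per arm. So 36 reproduces when 5.4 is the SD of a within-person difference. Section 4.4 uses it for morning against evening; I assume the same SD for active against sedentary.

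**Variance of the pooled contrast.** Let M, E and S be the morning, evening and sedentary scores, V = Var(M−S) = Var(E−S), and W = Var(M−E).

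- W = 2V − 2·Cov(M−S, E−S), so the covariance is V − W/2.
- Var((M+E)/2 − S) = (2V + 2(V − W/2))/4 = V − W/4.
- With equal variances and correlations W = V, so the variance is 0.75V = 0.75 × 29.16 = 21.87 and the SD is 4.68.
- 95% CI half-width at n = 36 (t = 2.03): 2.03 × 5.4/6 = 1.83 points for a separate comparison and 2.03 × 4.68/6 = 1.58 for the pooled one. The separate interval is about 15% wider.

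**Range.** Hold V at 5.4² and vary W/V. The correlation between the two separate contrasts is 1 − W/(2V). Power is for 2.6 points at both timings, n = 36; the last column is by simulation.

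| W/V | Variance saving | Pooled SD | Pooled power | Exactly one separate test significant |
|---|---|---|---|---|
| 0.25 | 6% | 5.23 | 0.83 | 11% |
| 0.5 | 12.5% | 5.05 | 0.85 | 16% |
| 1 | 25% | 4.68 | 0.90 | 23% |
| 1.5 | 37.5% | 4.27 | 0.94 | 28% |

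Each separate test has power 0.80 in every row.

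**Other true effects (W = V, n = 36, simulation of 200,000 trials).**

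| True benefit, morning / evening | Power of each separate test | Both significant | Exactly one | Pooled |
|---|---|---|---|---|
| 2.6 / 2.6 | 0.80, 0.80 | 69% | 23% | 0.90 |
| 2.0 / 2.0 | 0.58, 0.58 | 41% | 33% | 0.70 |
| 1.3 / 1.3 | 0.29, 0.29 | 15% | 29% | 0.37 |
| 0 / 0 | 0.05, 0.05 | 1% | 8% | 0.05 |
| 2.6 / 0 | 0.80, 0.05 | 4% | 78% | 0.37 |

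With no effect at either timing, at least one separate test is significant in 9.2% of trials, against 5.0% for the single contrast.

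**The case against.** The strongest reply is that the pooled contrast is a different estimand, not a sharper version of the planned one. It averages over timings, while the trial's hypothesis is that timing matters, and section 5.1.1 also ties the sedentary period to the timing question. If one timing gives 2.6 points and the other none, pooled power is about 37% against 80% for the effective timing. For phase outcomes such as DLMO or time of lowest temperature, opposite shifts could cancel in the average. This stands: a reader might infer that the pooled test should replace the two comparisons or cover every endpoint, and the documents do not support that.

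Second, one significant and one non-significant result do not contradict each other. The difference between the two contrasts is morning minus evening, which the primary analysis tests directly. That is also correct. If both intervals are kept, a split will be as frequent as before; what changes is that the exercise question has its own test.

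Third, a reader might infer a fixed loss of a quarter of the precision. That figure rests on a covariance structure that the documents do not state. If the two active periods resemble each other more than either resembles the sedentary one, the loss is smaller.

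Fourth, the unequal gaps (21 days after the sedentary ISI in one sequence, 42 in the other) might look like a further source of noise. The effect is negligible. A trend of 1 point per 3 weeks gives shifts of 1 or 2 points, adding variance 0.25 to 29.16 (0.9%); power moves from 80.2% to 79.9%.

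Fifth, bias limits this comparison more than precision does. With no exercise effect and a mean shift of 1 point since the sedentary period, the pooled test is significant in 24% of trials and each separate test in 19%. Pooling makes the confounded comparison more precise; it does not make it causal.

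**Conclusion.** The concern holds in limited form. Section 5.1.1 poses an activity-versus-no-activity question, and section 10.2 answers it only in two parts although both active scores are available. Adding the pooled contrast reduces the variance by 25% under equal variances and correlations, and by 6% to 37.5% over the range examined. At 2.6 points at both timings, power rises from 0.80 to 0.90 (0.83 to 0.94); at 2.0 points, from 0.58 to 0.70 under equal correlations. These figures assume that 5.4 applies to active-minus-sedentary differences, that 36 participants complete, and that both timings work about equally.

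A reader might infer that the pooled test would settle whether the exercise worked. It would not. The sedentary period always comes first, after selection on ISI ≥ 10, so time trend and regression to the mean affect the pooled and separate contrasts alike. Nor does the point reach the primary test or the sample size. It is a cheap improvement to a sensitivity analysis, not a flaw in the main comparison.

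**What to change.** In section 10.2:

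- Add a paired analysis of (morning + evening)/2 minus sedentary for the ISI, named as the test of activity versus no activity.
- Apply it to secondary endpoints where an average over timings is meaningful. Exclude phase and diurnal-pattern outcomes such as DLMO and time of lowest temperature.
- Keep both planned pairwise comparisons, with 95% confidence intervals, as the timing-specific results.
- State that the sedentary period always comes first, so that time trend and regression to the mean affect all three contrasts and pooling improves precision only.

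The cost is a few sentences and one more test per endpoint, with no new data and no added burden for participants. The downside is low power for the pooled contrast (about 37%) if only one timing works, which is why the pairwise comparisons stay.
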